9.1.2. Incidence of Adverse Events

Incidence of pretreatment AEs and TEAEs will be summarized by the number and percentage of participants with at least one AE. The number and percentage of participants will also be presented by system organ class (SOC) and preferred term (PT). At each level of summarization, a participant will be counted once if the participant reported one or more

events. Percentages will be calculated based on the number of participants in the Safety population. The summary will be presented alphabetically by SOC and within each SOC, by decreasing total incidence of PT. If the incidence for any two or more PTs is equal, the PTs will be presented in alphabetical order.

9.1.3. Severity of Adverse Event

A summary of pretreatment AEs and TEAEs by severity (“Mild”, “Moderate” and “Severe”) as assessed by the Investigator will be presented by SOC, PT, and severity in a manner similar to that described in Section 9.1.1. In the severity table, if a participant reported multiple occurrences of the same AE, only the most severe will be presented. Percentages will be calculated based on the number of participants in the Safety population.

If severity is missing for an AE, all efforts should be made to obtain the severity from the Investigator. If it is still missing after all efforts, then a severity of “Mild” will be assigned for pre-treatment AEs and a severity of “Severe” will be assigned for TEAEs. The imputed values for the missing severity assessment will be used for the incidence summary, while the actual missing values will be presented in listings.

All severe AEs will be presented in a listing for participants in Safety population, and AEs will be flagged to denote pretreatment AEs and TEAEs.

9.1.4. Relationship of Adverse Events to Study Drug

A summary of TEAEs by relationship (“Related” and “Unrelated”) to study drug per investigator will be presented by SOC, PT, and relationship in a manner similar to that described in Section 9.1.1. Percentages will be calculated based on the number of participants in the Safety population.

If a participant reported more than 1 TEAE within an SOC or PT, then the TEAE with the strongest causality relationship to study drug per investigator within each SOC and each PT will be included. If the relationship to study drug is missing for a TEAE, all efforts should be made to obtain the relationship from the Investigator. If it is still missing after all efforts, a study drug causality of “Related” will be assigned for TEAEs. The imputed values for the missing relationship to study drug will be used only for incidence summary, while the actual missing values will be presented in listings.

All drug-related AEs will be presented in a listing for the Safety population, and AEs will be flagged to denote pretreatment AEs and TEAEs.

9.1.5. Serious Adverse Events

Serious TEAE will be presented by SOC and PT in a manner similar to that described in Section 9.1.12. Percentages will be calculated based on the number of participants in the Safety population.

All participants in the Safety population who have an SAE will be presented in a listing and AE will be flagged to denote pretreatment AEs and TEAEs.

9.1.6. Adverse Events Leading to Study Drug Discontinuation

A summary of study drug discontinuations due to TEAE (that is, participants who have a TEAE with a study treatment action taken of “Drug Withdrawn”) will be presented by SOC and PT in a manner similar to that described in Section 9.1.1. At each level of participant summarization, a participant is counted once if the participant reported one or more events. Percentages will be calculated based on the number of participants in the Safety population.

All participants in the Safety population who have an AE leading to study drug discontinuations or an AE leading to study discontinuation (that is, participants who answer “Yes” to the question of “Caused Study Discontinuation”) will be presented in a listing and AEs will be flagged to denote pretreatment AEs and TEAEs.

9.1.7. Death

All participants in the Safety population with an AE leading to death (that is, participants who have an AE with an outcome of “Death Related to Adverse Event”) will be presented a listing and AEs will be flagged to denote pretreatment AEs and TEAEs.

9.1.8. Adverse Events of Special Interest (AESIs)

A summary of AESIs as collected in the eCRFs will be presented by SOC and PT in a manner similar to that described in Section 9.1.1. At each level of participant summarization, a participant is counted once if the participant reported one or more events. Percentages will be calculated based on the number of participants in the Safety population within the subgroup category.

All participants in the Safety population who have an AESIs will be presented in a listing

9.2. Clinical Laboratory Evaluations

Tests detailed in **Table 1** will be performed by the Study Center and sent to the Central laboratory as scheduled in **Table 3**. Participants will fast for 3 to 4 hours before safety laboratory sample collections.

Descriptive statistics for observed values (SI unit) at each scheduled visit and changes from baseline at each scheduled post-baseline visit will be summarized for clinical laboratory tests with numeric values for participants in the Safety population. For urinalysis, summary tables will be performed as data permit.

All laboratory data will be presented in listings for participants in Safety population and abnormal values will be flagged.

Pregnancy test lab data will be presented in a listing for female participants in Safety population.

Table 1 Protocol-Required Safety Laboratory Assessments

Assessment	Parameter					
Hematology	Hematocrit	RBC indices:		WBC count w/differential:		
	Hemoglobin	-- MCH	-- Basophils	-- Monocytes		
	Platelet count	-- MCV	-- Eosinophils	-- Neutrophils		
	RBC count	-- %Reticulocytes	-- Lymphocytes			
Clinical chemistry (serum)	Alkaline phosphatase	BUN	Creatine kinase	Potassium		
	ALT/SGPT	Calcium	GGT	Protein (total)		
	AST/SGOT	Creatinine	Glucose (fasting)	Sodium		
	Bilirubin (total, direct)					
Coagulation	aPTT	INR	Prothrombin time			
Routine urinalysis	Specific gravity pH, glucose, protein, blood, ketones, bilirubin, urobilinogen, nitrite, leukocyte esterase by dipstick Microscopic examination (if blood or protein is abnormal)					
Additional tests	Follicle-stimulating hormone and estradiol (women of nonreproductive potential, only) ¹ Human chorionic gonadotropin (hCG) pregnancy test (for women of reproductive potential, only) ² Urine drug screen: amphetamines, cocaine, opiates, and cannabinoids ¹					

ALT=alanine aminotransferase; aPTT=activated partial thromboplastin time AST=aspartate aminotransferase; BUN=blood urea nitrogen; GGT=gamma glutamyl transferase; INR=international

normalized ratio; MCH=mean corpuscular hemoglobin; MCV=mean corpuscular volume; RBC=red blood cell; SGOT=serum glutamic-oxaloacetic transaminase; SGPT=serum glutamic-pyruvic transaminase; WBC=white blood cell

Note: All events of ALT $\geq 3 \times$ upper limit of normal (ULN) and bilirubin $\geq 2 \times$ ULN ($>35\%$ direct bilirubin) or ALT $\geq 3 \times$ ULN and international normalized ratio (INR) >1.5 , which may indicate severe liver injury (possible Hy's Law), must be reported as an SAE.

¹ Test is necessary at the Screening Visit, only

2 Pregnancy tests will be serum based at Screening and at the Follow-up Visit. Urine-based tests are acceptable for all other visits, unless serum testing is required by local regulation or IRB/IEC.

9.3. Vital Sign Measurements

Supine Blood Pressure (BP), orthostatic BP and pulse, respiratory rate, oxygen saturation, and temperature will be performed as scheduled in **Table 3**.

Descriptive statistics (include 95% CI of means) for observed values at each scheduled visit and changes from baseline at each scheduled post-baseline visit will be summarized for respiratory rate, oxygen saturation, and temperature tests. Observed values and changes from baseline by position (supine, standing) at each scheduled visit will also be summarized for Systolic Blood Pressure (SBP), Diastolic Blood Pressure (DBP), Mean Arterial Pressure (MAP), and pulse for participants in the Safety population.

Descriptive statistics (including 95% CI of means) for observed values by position (supine, standing and orthostatic) at each scheduled visit will be summarized for SBP, DBP, MAP, and pulse. Mean and 95% CI plots in observed value of SBP, DBP, MAP, and pulse will be presented over time.

The number and percentage of participants who meet the potentially clinically important (PCI) criteria presented in **Table 2** at any postdose timepoint will be summarized.

Percentages will be calculated relative to the number of participants with non-PCI baseline values and at least 1 assessment in the corresponding post-baseline period. The numerator will be the total number of participants with available non-PCI baselines and at least 1 PCI value in the postbaseline period.

Table 2 Criteria for Vital Signs Results

Vital Sign Parameter	Flag	PCI Criteria
		Observed Value
Supine/Standing Systolic Blood Pressure (mmHg)	High	≥ 180
	Low	≤ 90
Supine/Standing Diastolic Blood Pressure (mmHg)	High	≥ 105
	Low	≤ 60
Supine/Standing Pulse Rate (bpm)	High	≥ 110
	Low	≤ 50
Orthostatic Systolic Blood Pressure (mmHg)	Decrease	≥ 20
Orthostatic Diastolic Blood Pressure (mmHg)	Decrease	≥ 10
Orthostatic Pulse (bpm)	Increase	≥ 30

All vital signs data will be listed for the Safety population.

9.4. Physical Examination

At Screening and Follow-up visit, a complete physical examination will be performed by the Investigator and documented on the appropriate eCRF. All other examinations may be symptom directed at the Investigator's discretion. A complete physical examination will include examination and assessment of the following:

General appearance	Lymph nodes	Nervous system
Cardiovascular system	Head, eyes, ears, nose, and throat	Skin
Respiratory system	Neck	Mental status
Abdomen/liver/spleen	Musculoskeletal system	

Breast, genitourinary, and rectal examinations are optional and may be performed at the discretion of the Investigator.

Physical examination results for all participants in the Safety population will be presented in a listing.

9.5. Electrocardiogram

All ECGs must be obtained after the participant has rested supine for ≥ 5 minutes and should be obtained before blood draws (or ≤ 10 m after a blood draw, if necessary). When timing coincides, ECGs and vital signs can be assessed together.

If a QTc result (corrected using Fridericia's formula) is outside of the normal range (>450 ms), the ECG should be repeated twice and the average of the 3 results calculated.

Descriptive statistics for observed values and changes from baseline will be summarized for ventricular rate (bpm), PR Interval (msec), QRS Duration (msec), QT Interval (msec), QTc Interval (msec), QTcF Interval (msec) for participants in the Safety population at each scheduled visit in 3. All ECG results for all participants in the Safety population will be presented in a listing.

The number and percentage of participants with absolute QTcF intervals in the following categories will be examined overall and by sex: QTcF ≤ 450 msec, 450 msec $<$ QTcF ≤ 480 msec, 480 msec $<$ QTcF ≤ 500 msec, and QTcF > 500 msec. Shift tables will be presented comparing values between baseline and EOT visit as well as baseline and end of study visit.

The number and percentage of participants with increase from baseline QTcF intervals in the following categories will be examined overall and by sex: QTcF interval increases by >30 msec, but ≤ 60 msec, and QTcF interval increases by >60 msec.

The number and percentage of participants with ECG interpretations at each scheduled visit for the Safety population will be presented. Interpretation results include Normal, Abnormal Not Clinically Significant, Abnormal Clinically Significant and Not Done.

9.6. Other Safety Data

9.6.1. Echocardiogram

All data for participants in the Safety population who have Screening Echocardiogram will be presented in a listing.

9.6.2. Suicidality

The Columbia Suicidality Severity Rating Scale (C-SSRS) will be administered according to 2, starting pre-dose on Day 1 of the Treatment Period and at all subsequent visits where clinical assessments are conducted, including at any unscheduled visit.

The C-SSRS (1) contains two required items pertaining to suicidal ideation, four required items pertaining to suicidal behavior, and one required item pertaining to non-suicidal self-injurious behavior. There are eight additional suicidal ideation items and two additional suicidal behavior items which are completed in cases of positive responses for other items, as well as two items for suicide and suicide behavior present during the interview. Most items are rated on a dichotomous scale (yes or no) or 5-point Likert scale. In addition, the total number of attempts is recorded. In the event of a positive categorical response the interviewer can provide text or narrative that further describes the thought or behavior.

Two versions of the C-SSRS are used in this study:

- The “Baseline/Screening” version will be administered at the Day 1 visit and will be completed for all participants. It includes questions about suicidal ideation in the past 12 months or lifetime history.
- The “Since Last Assessment” version will be completed for all participants at all study visits after the Day 1 Visit.

The number and percentage of participants with a positive response for suicidal ideation and suicidal behavior will be summarized by participants in Safety population at each scheduled visit and overall. Total number of attempts for each suicidal behavior will be summarized for participants in Safety population at each scheduled visit and overall.

Listings of the C-SSRS data will be provided for participants in the Safety population with a positive response for suicidal ideation and/or suicidal behavior.

10. Clinical Outcomes Assessments/Participant Questionnaires

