10.2.3. Adverse Events of Special Interest (AESIs)

Based on the mechanism of action of sGC and anticipated vasodilation effects and based on the fact that IW-6463 is a CNS-penetrant stimulator of sGC, the Sponsor will collect AESIs in a timely manner.

The AESIs relate to symptomatic hypotensive events and/or tachycardia, dizziness, syncope, and TEAEs related to change of neurobehaviors (ie, suicidality or euphoria). In addition, because riociguat, a marketed sGC stimulator, includes bleeding events as a warning and precaution on its prescribing information ([15](#)), bleeding events will also be considered AESIs for IW-6463 in

this study. The specific list of TEAE terms will be provided in the C6463-201 safety management plan.

An AESI classification means that although an event might be nonserious, it will nonetheless be reported to the Sponsor by completing an SAE form, filling in the AESI box, and submitting to Syneos Health (see Section 10.1.1) within 5 business days of the Investigator's awareness of the event.

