7.2.2. Treatment Compliance and Modifications

Compliance is defined as the total dosage taken divided by the total dosage expected to be taken, times 100. The treatment compliance will be summarized for all participants in the Safety population. Compliance rates will also be categorized as missing, <80%, ≥80% and ≤120%, and >120% and will be summarized. Overall compliance will be listed for all participants in the Safety population.

8. Efficacy Analysis

Not applicable.

9. Safety Analysis

If not otherwise specified, the safety analyses will be performed using the Safety population. If not otherwise specified, the baseline value is defined as the last non-missing value measured (scheduled or unscheduled measurements) before administration of study drug on Day 1.

If there is more than 1 safety measurement (e.g., for a lab endpoint) at a postbaseline timepoint, only the last measurement will be used for by visit summary. All postbaseline assessments including unscheduled assessments, if any, will be used for shift tables, and all assessments will be presented in listings.

A listing of all participants affected by the coronavirus disease (COVID-19) related study disruption will be presented for participants in Safety population.

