9.1. Adverse Events

Adverse events will be coded using MedDRA Version 24.0.

Pretreatment AEs are defined as AEs with a start date between the informed consent date and the date of the first dose of study drug.

Treatment-emergent AEs are defined as AEs reported in the clinical database with a start date on or after the first dose of study drug until the end of the follow-up period.

An overall summary of the number of participants in the Safety population with AEs will be presented, including the number and percentage of participants with AEs, pretreatment AEs, TEAEs, severe TEAEs, drug-related TEAEs, serious AEs, AEs leading to death, TEAEs leading to study drug discontinuation and Treatment-emergent adverse events of special interest (AESIs).

All AEs will be presented in listings for the Safety population, and AEs will be flagged to denote pretreatment AEs and TEAEs. Incomplete AE start dates will be imputed as described in Section 16.2.

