16.1. Schedule of Study Procedures

Table 3: Schedule of Events

Study Period →	Screening	Treatment Period (assessments are predose unless noted)						F/U
		In-clinic Screening	In-clinic Visit	At-home Visit ¹	At-home Visit ¹	In-clinic EOT Visit ²		
Visit Type/Name →	In-clinic Screening	Day 1	Day 8 (±2 days)	Day 15 (±2 days)	Day 29 (-4 days)		Day 43 (±4 days)	
					Pre	2 h	4 h	6 h
Visit Day (window) →	Day -28 (-28 to -10 days)				(-30 m)			
Study Procedure ↓								
ICF signed	X							
Eligibility evaluation	X	X						
Demographics	X							
Drug/alcohol screen ²	X							
Medical history	X	X						
Physical examination ³	X	X	X	X	X			X
Weight (W), height (H)	W, H	W		W	W			W
12-lead ECG ⁴	X	X			X			X
ECHO ⁵	X							
BP (including orthostatic) & pulse ⁶	X	X	X	X	X		X	X
Oral temp, O ₂ , & RR	X	X	X	X	X		X	X
Clinical safety samples ⁷ (chemistry, coag/hematology, UA)	X	X ⁸	X	X	X			X
Pregnancy test ⁹	X	X	X	X	X			X
C-SSRS		At each scheduled and unscheduled visit						
Study drug supply/accountability/return ¹⁰		X	X	X	X			
Participant diary	Issued at Screening; reviewed at each scheduled visit; collected at Follow-up							

Study Period →	Screening	Treatment Period (assessments are predose unless noted)					F/U						
		In-clinic Screening	In-clinic Visit	At-home Visit ¹	At-home Visit ¹	In-clinic EOT Visit ²							
Visit Day (window) → Study Procedure ↓	Day -28 (-28 to -10 days)	Day 1	Day 8 (±2 days)	Day 15 (±2 days)	Day 29 (-4 days)		Day 43 (±4 days)						
					Pre	2 h	4 h	6 h					
					(±30 m)								
Study drug dosing ^{10,11}		QD Days 2–28, including at home, at a consistent time (±1 h of Day 1 dose time)		In clinic									
AE/SAE evaluation	From Screening through Follow-up												
Prior/concom. med. rev.	From Screening through Follow-up												
Blood sample for PK			X	X	X	X	X						
CSF sample for PK							X						
Blood sample for PD biomarkers ⁷	X	X		X	X		X						
Neuroimaging ¹²	X	X				X							
MFIS		X			X								
PGIC					X								
PROMIS–Cognitive function		X			X								
Visit discharge ¹³		~4h post											
Study completion							X						

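### Does the undefined overall row in the C-SSRS summary hide how many participants become positive after dosing?

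*SAP*

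**What the plan says.** SAP 9.6.2 plans two C-SSRS summaries. Participants with a "positive response for suicidal ideation and suicidal behavior will be summarized by participants in Safety population at each scheduled visit and overall". Separately, "Total number of attempts for each suicidal behavior will be summarized for participants in Safety population at each scheduled visit and overall". The section does not say which period, visits or form version the overall figure covers.

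Two versions of the scale are used. The Baseline/Screening version is given before dosing on Day 1, and "It includes questions about suicidal ideation in the past 12 months or lifetime history". The Since Last Assessment version is used at every visit after that. The schedule in SAP 16.1 places the C-SSRS "At each scheduled and unscheduled visit".

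The same section plans a listing of C-SSRS data for every Safety-population participant with a positive response. Protocol 9.3.8 specifies no C-SSRS analysis, so SAP 9.6.2 is where the summary is defined. SAP Section 1 adds that the specifications for tables, figures and listings are held in a separate document.

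**The concern.** The study has one arm and the sentence names no subgroup, so an overall figure placed after a by-visit one most naturally means across all visits. Day 1 is one of those visits. On that reading a participant whose only positive answer concerns events before any dose is counted alongside one who became positive on treatment. The attempts total has the same feature, and the SAP states no look-back for behavior or attempts on the Day 1 form.

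Elsewhere the SAP draws the line at first dose. Vital-sign flags are calculated "relative to the number of participants with non-PCI baseline values and at least 1 assessment in the corresponding post-baseline period", and treatment-emergent events are those "with a start date on or after the first dose of study drug until the end of the follow-up period". Nothing similar appears for the C-SSRS.

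Unscheduled visits add a second doubt. The opening of SAP Section 9 says "All postbaseline assessments including unscheduled assessments, if any, will be used for shift tables", and no C-SSRS shift table is planned. A positive found only at an unscheduled visit therefore has no obvious place in the by-visit rows.

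Safety is the primary objective, Protocol 8.3.7 describes the drug as CNS-active, and the AESIs include "TEAEs related to change of neurobehaviors (ie, suicidality or euphoria"). A reader of the table might not be able to tell history from on-treatment response.

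**Working it through.** The plan gives no C-SSRS rate or count to reproduce, so the check asks what each reading of the overall row would let a reader recover. All counts below are assumed.

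**Inputs**
- Scheduled visits after Day 1: Days 8, 15, 29 and 43, so four (SAP 16.1).
- Denominator: the Safety population, planned at about 20 (Protocol 4.3), with at most 20 treated (SAP 4.1). The figure of 12 is the evaluable target and is not this table's denominator.
- H = participants positive on the Day 1 form. P = distinct participants positive at any later assessment.

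**1. Later visit rows alone.** With counts c1 to c4, max(c) ≤ P ≤ min(sum of c, N). For one positive at each visit, P lies between 1 and 4, that is 1/20 = 5% to 4/20 = 20%. The rows alone do not fix P.

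**2. Overall includes Day 1.** The row lies between max(H, P) and min(H + P, N). Overall minus H is exactly the number positive later who were negative on Day 1, provided Day 1 forms are complete; SAP 9.6.2 has them completed for everyone. Take H = 2, one positive at each later visit, and overall = 3:
- new positives = 3 − 2 = 1;
- 0, 1 or 2 of the Day 1 positives may also recur, so P = 1, 2 or 3, which is 5%, 10% or 15% of 20.

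The literal row therefore gives new positives exactly and leaves open only how many with prior history were positive again.

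**3. Overall means after Day 1 only.** The same 3 gives P = 3, or 15%, directly.

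**4. How misleading could the literal row look?** With H = 4 and P = 1, overall is 4 or 5 (20% to 25%) against 1 (5%) after dosing. With H = 4 and P = 0, overall is 4 (20%) against 0. In the second case the table itself shows 4 on Day 1 and 0 at each later visit, so the source of the 20% is plain.

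**5. Attempts.** These are events, and the later form covers successive intervals that do not overlap. If Day 1 is included, overall attempts minus Day 1 attempts gives the post-Day-1 total exactly.

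**6. Unscheduled visits.** The Section 9 sentence goes on to send all assessments to listings. Section 9 also does not state that unscheduled records are barred from by-visit summaries; it says the last measurement is used when a timepoint has more than one. A positive at an unscheduled visit is therefore displayed whichever way the overall row is built.

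**The case for a change.** The strongest case for a change is that the text is ambiguous and a sentence would cure it. Neither SAP Section 4 nor the opening of Section 9 defines the overall row. The SAP separates baseline from post-dose findings for vital signs and adverse events, so doing the same for suicidality would be consistent. AESI and TEAE tables count adverse-event records, and a positive answer on the scale need not have become one. With at most 20 treated, each participant is at least 5 percentage points.

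Much of this stands. The row is undefined. Under the literal reading the table alone does not give the number of distinct post-dose positives when a participant may be positive both on Day 1 and later. The AESI tables do not replace a C-SSRS count.

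It does not follow that the plan contains no post-dose participant count. That holds only if Day 1 is included; on the other reading the overall row is that count. Nor is history hidden, since Day 1 is a scheduled visit with its own row and the form version follows the visit. The look-back for behavior and attempts is a property of the named form, and the SAP sentence about ideation does not claim to describe the whole form.

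**Conclusion.** This is missing detail that analysts would fill sensibly, so no change to the plan is called for. Under either reading the planned outputs carry useful information: new positives by subtraction, or post-dose positives directly. What remains uncertain is a label and, in the assumed example, whether 1, 2 or 3 of 20 participants were positive after dosing. The planned listing answers that person by person. The C-SSRS is not a named primary endpoint, and suicidality reported as an adverse event is summarised separately as an AESI.

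This conclusion rests on three assumptions: the listing identifies the visit of each response, Day 1 forms are complete, and the Safety population is close to the planned 20. Fewer treated participants would make each percentage larger but the listing shorter. The separate table specifications could not be seen and may already settle the definition. No safety conclusion depends on which reading is used.
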